- proportions of patients who achieve clinic-based FEV₁ $\geq 80\%$ predicted at weeks 12, 16, and at endpoint
- proportions of patients who achieve forced expiratory flow at 25% to 75% of forced vital capacity (FVC) (FEF₂₅₋₇₅) $\geq 70\%$ predicted at weeks 12, 16, and at endpoint
- proportions of patients who achieve FEV₁:FVC ratio ≥ 0.80 at weeks 12, 16, and at endpoint

The repeated measures logistic regression model with treatment group, corresponding baseline parameter value, prior therapy use, week, and week-by-treatment group interactions in the model and with an unstructured covariance matrix will be used. In the case of convergence issues with the unstructured covariance form, the exchangeable covariance matrix will be used. The weekly probability estimates of achieving the improvement criterion in each treatment group, as well as the estimates of weekly odds ratios comparing each TEV-53275 treatment group versus placebo with corresponding 95% CI and p-values will be derived.

All repeated measures model will be run including measurements at all visits/weeks through week 16.

For changes from baseline in weekly average of rescue medication use over 12 weeks from week 1 through 12 and over 16 weeks from week 1 through 16, and changes from baseline in percentage of asthma control days (no symptoms and no rescue medication use) over 12 weeks from week 1 through 12 and over 16 weeks from week 1 through 16, Wilcoxon rank-sum test will be used stratified on randomization stratification factors.

The frequency of CAEs will be analyzed using a negative binomial regression method including randomization stratification factors and treatment group in the model and the logarithm of follow-up time as an offset variable. The ratio of CAE rate between the treatment groups and its 95% CI will be estimated from the negative binomial regression model. Treatment effects will be tested using the likelihood-based Chi-square test.

The Kaplan-Meier method will be used to estimate and compare the distributions of time to the first CAE between treatment groups. Distribution difference will be compared by a log rank test adjusting for the randomization stratification factors.

Multiple Comparisons and Multiplicity: No adjustments will be made for the preplanned multiple comparisons/endpoints.

Safety Analyses: The safety of TEV-53275 will be assessed throughout the study by evaluating adverse events, clinical laboratory test results, vital signs measurements, electrocardiogram (ECG) findings, physical examination results, local tolerability and pain, and concomitant medication usage. Protocol-defined adverse events of special interest (PDAESI) include systemic severe reactions (including anaphylaxis), injection site findings, opportunistic infections, helminth infections, and malignancies.

Safety analyses will be performed on the safety analysis set.

All adverse events will be coded using the Medical Dictionary for Regulatory Activities (MedDRA). Each patient will be counted only once in each preferred term or system organ class (SOC) category for the analyses of safety. Summaries will be presented for all treatment-emergent adverse events (overall and by severity), adverse events determined by the investigator to be related to test IMP/non-IMP (ie, reasonable possibility) (defined as related or with missing relationship) (overall and by severity), serious adverse events, and adverse events causing withdrawal from the study. Summaries will be presented by treatment group and for all patients. Patient listings of all adverse events, serious adverse events and adverse events leading to withdrawal will be presented.

Values and changes from baseline in clinical laboratory, ECG, and vital signs measurement data (including the incidence of abnormalities) will be summarized descriptively.

Local tolerability at the injection site (erythema, ecchymosis, induration, tenderness, warmth, and swelling, and pain) will be assessed using standardized scales and summarized descriptively.

The use of concomitant medications will be summarized by therapeutic class using descriptive statistics.

For continuous variables, descriptive statistics (n, mean, standard deviation [SD], standard error, median, minimum, and maximum) will be provided for actual values and changes from baseline to each time point. For categorical variables, patient counts and percentages will be provided.

Pharmacokinetic Analysis: Summaries of TEV-53275 serum concentrations will be presented by nominal time point and dose. Plots of individual TEV-53275 serum concentrations will be presented by actual day (linear and log scales). Plots of mean or median TEV-53275 serum concentrations will be presented by nominal day (linear and log scales).

Pharmacodynamic/Biomarker Analysis: Blood eosinophil count and serum IL-5 (free and total) levels will be summarized by treatment and time point using descriptive statistics. Individual data will be listed.

Immunogenicity Analysis: Anti-TEV-53275 antibody information, number and percent of patients positive for ADA and their antibody titers, and the number of ADA positive patients who are positive for neutralizing antibody, will be described. The impact of the presence of ADA on pharmacokinetics, efficacy, and clinical safety will be evaluated, if appropriate, and results will be provided in the clinical study report.

Ancillary Studies Analysis: During the run-in and treatment periods of this study, patients will be supplied with ProAir Dihaler. Data from these inhalers will be collected centrally.

Planned Interim Analysis: The final primary efficacy analyses will be performed when all patients have completed V9 (week 16) or withdrawn from the study. An unblinded interim analysis is planned, when approximately 120 patients (40 patients per arm) have completed the week 8 visit or withdrawn from the study, to assess the early efficacy data. The objectives of the unblinded interim analysis are 1) to detect an early efficacy success signal; 2) to conduct a formal futility analysis, and; 3) to evaluate early stopping criteria.

It is of note that meeting the interim efficacy success criterion will not result in terminating the study early. The early efficacy success result, combined with satisfactory safety data, may assist with preparation / initiation of further safety and efficacy studies, and enable communications with regulatory agencies regarding further clinical development. However, meeting the study futility criterion may result in early termination of the study due to futility.

At the time of the interim analysis, a blinded safety analysis will be conducted. If there is any safety signal of concern at the time of the interim analysis, unblinded safety analyses may be warranted.

Further, due to challenges in patient enrollment in the face of the COVID-19 pandemic, the feasibility of an early stopping of the trial with smaller sample sizes may also be evaluated during the interim analysis. The feasibility analysis will be described in the statistical analysis plan.

For the early efficacy success and futility analysis, the week 8 efficacy endpoint, ie, change from baseline at week 8 in morning trough FEV1, will be analyzed. The same Bayesian analysis for the final primary efficacy analysis will be applied, and both the early success and futility criteria will be based on the derived posterior probability of the TEV-53275 dose group performing better than the placebo in improving the week 8 endpoint.

The execution of the unblinded interim analysis

The unblinded interim analysis will be conducted by independent, unblinded statistician(s) and programmer(s) who are not part of the study team, following the pre-specified algorithms and rules. An independent unblinded data review committee will be set up to review the unblinded interim efficacy analysis results. A group of the sponsor's management team, who are not a part of the study team, may have access to the unblinded interim analysis results. In order to maintain the study blind and the study conduct integrity, a data review charter will be finalized prior to the interim analysis, which specifies the processes for securely unblinding the interim analysis results. The processes will be followed to ensure that the study blind will be maintained in the blinded study personnel who are involved in managing the study activities until the study is unblinded at the final analysis. This charter will also detail the blinded safety review.

TABLE OF CONTENTS

TITLE PAGE	1
DOCUMENT HISTORY	2
SPONSOR PROTOCOL APPROVAL	3
INVESTIGATOR AGREEMENT	4
CLINICAL STUDY PROTOCOL SYNOPSIS	5
TABLE OF CONTENTS	27
LIST OF ABBREVIATIONS AND DEFINITIONS OF TERMS	34
1. INTRODUCTION AND BACKGROUND INFORMATION	39
1.1. Introduction	39
1.1.1. Interleukin 5	39
1.1.2. TEV-53275	39
1.1.3. TEV-53275 and Asthma	39
1.1.4. Purpose of the Study	40
1.2. Findings from Nonclinical and Clinical Studies	40
1.2.1. Nonclinical Studies	40
1.2.1.1. Pharmacology	40
1.2.1.2. Pharmacokinetics	40
1.2.1.3. Nonclinical Safety	41
1.2.2. Clinical Studies	42
1.2.2.1. Study TV53275-PK-10152	42
1.3. Known and Potential Benefits and Risks to Patients	44
1.3.1. Known and Potential Benefits and Risks of the Test Investigational Medicinal Product(s)	44
1.3.2. Overall Benefit and Risk Assessment for This Study	45
2. STUDY OBJECTIVES AND ENDPOINTS	46
2.1. Primary and Secondary Objectives and Endpoints	46
2.1.1. Justification of Primary Endpoint	47
2.2. [REDACTED]	47
3. STUDY DESIGN	50

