After obtaining informed consent, a screening period of up to approximately 2 weeks is allowed. Patients may be evaluated for inclusion into the run-in period during the screening period. An absolute eosinophil count of ≥ 300 cells/ μ L is required to participate in the study. A complete blood count (CBC) will be obtained and may be repeated once during the screening period to demonstrate an absolute eosinophil count of ≥ 300 cells/ μ L (a total of 2 attempts during the screening period). Other laboratory testing, medical history assessments, blood collection for biomarkers, physical examination, and other assessments will be completed during the screening period and may be conducted at more than one visit.

Formal pulmonary function testing (spirometry and reversibility testing) will be conducted in the morning between 0530 and 1100 hours using the study-provided spirometry equipment. Testing will be performed in the clinic unless specified as by handheld device. Patients are required to withhold asthma maintenance medications prior to any formal pulmonary function testing. If the patient has taken asthma maintenance medication within 24 ± 2 hours for medication dosed once daily (QD), or within 12 ± 2 hours for medications dosed more frequently than once daily or has taken short-acting β_2 -adrenergic agonist (SABA) rescue medication within 6 hours or inhaled corticosteroid in combination with long-acting β_2 -adrenergic agonist (ICS/LABA) used as rescue medication within 12 hours of the planned pulmonary function testing, the visit must be rescheduled. Patients who meet the pre-albuterol/salbutamol lung function requirements may undergo reversibility testing approximately 30 minutes after 4 inhalations of albuterol/salbutamol hydrofluoroalkane (HFA) inhalation aerosol (90 μ g ex-actuator or equivalent). Patients who demonstrate reversibility $\geq 12\%$ and a ≥ 200 mL increase in forced expiratory volume in 1 second (FEV₁) from baseline may enter the run-in period if they meet other eligibility requirements as specified.

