Supportive Analysis: The frequentist approach will be used for analyzing the primary efficacy endpoint as a supportive analysis. The same estimand with respect to study population, efficacy endpoint and ICES along with the same handling strategies will be applied. The population-level summary statistics will be the least squares means in the treatment groups derived from the mixed-effects model for repeated measures (MMRM).

The MMRM model will include baseline morning trough FEV₁, the randomization stratification factor (prior therapy use), baseline eosinophil count visit (weeks 2, 4, 8, 12, and 16), treatment group, and visit-by-treatment group interactions. Contrasts for pairwise treatment comparisons of interest will be constructed. The unstructured covariance matrix will first be used; however, in case of convergence issues, the compound symmetry covariance matrix structure will be used instead.

Missing data are expected to occur due to early dropouts from study or “analysis dropouts” resulting from the use of additional or alternative medications and COVID-19 infections, as mentioned above. We plan to use the reference-based multiple imputations method ([Mallinckrodt et al 2017](#)) to handle the missing data problem. This approach imputes missing data based on regression models from the placebo-treated patient data, representing a missing not at random (MNAR) mechanism. It is expected to yield a conservative treatment effect estimate as compared to the estimate obtained from multiple imputations (MI) under a missing at random (MAR) mechanism. This approach has recently been successfully applied in a Phase 3 pediatric trial comparing fluticasone propionate multidose dry powder inhaler (MDPI) with fluticasone propionate/salmeterol MDPI (Study FSS-AS-30003). More details on implementing the reference-based MI will be provided in the protocol and statistical analysis plan.

The Rubin’s method will be used to combine estimates from multiply-imputed datasets. The final estimated treatment differences will be presented together with the 2-sided 90% confidence intervals (CI) and p-values.

Sensitivity Analyses: The primary efficacy analysis and supportive analysis will be repeated using the PP population.

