2.4. Sample Size and Power Considerations

The sample size is calibrated based on simulation studies to assess the operating characteristics of the following Bayesian success criterion for the final analysis of the primary efficacy endpoint: adjusted mean change from baseline at week 12 in trough FEV₁:

With the same base assumptions (treatment effect=0.1L and SD=0.35L), the comparison between the 1200 mg treatment group vs placebo using a two-sample t-test at one-sided alpha of

² CinqAir® is a registered to Teva Pharmaceutical Industries Ltd.

15% would provide a study power of 80.6%. The statistical software East version 6.5 was used for the calculation.

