4.2. Specification of Baseline Values

Unless otherwise specified, baseline value is defined as the last observed value before the administration of IMP.

The baseline for hand-held spirometry parameters and e-diary variables will be the average of the values over the 7 days preceding day of randomization.

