6.2.4.2. Supportive Analysis

The frequentist approach will be used for analyzing the primary efficacy endpoint as a supportive analysis. The primary estimand with respect to treatment condition, study population, efficacy endpoint and ICEs along with the ICE handling strategies will be applied. Both the multiple imputation method and the reference-based multiple imputations method will be used to handle

the missing data. The population-level summary statistics will be the combined least squares means in the treatment groups and the combined least squares mean treatment differences derived from analyses of the multiply imputed datasets using the mixed-effects model for repeated measures (MMRM).

The MMRM model will include baseline morning trough FEV₁, the randomization stratification factors (prior therapy use and absolute eosinophil count at screening), visit (weeks 2, 4, 8, 12, and 16), treatment group, and visit-by-treatment group interactions. Contrasts for pairwise treatment comparisons of interest will be constructed. The unstructured (UN) covariance structure will first be used; however, in the case UN covariance structure does not converge, the compound symmetry (CS) covariance structure will be used.

The Rubin's method will be used to combine estimates from multiply-imputed datasets. The final estimated treatment differences will be presented together with the 2-sided 90% CI and p-values.

[figure not shown]
MI steps and SAS example codes are as follows:

Step 1: Following observations will be considered as “analysis dropouts” and be excluded from the analysis (set to missing)

- observations after the use of asthma maintenance medications (regardless of availability of data obtained afterwards);
- observations that occurred after the diagnosis of COVID-19 infections.

[figure not shown]
For all early dropouts and “analysis dropouts”, regardless of assigned treatment arm, missing imputation will be based on data from the placebo-treated patients (eg, reference-based imputation).

Step 2: Missing data will be imputed with 100 imputations using multiple imputation and reference-based multiple imputations. The same sample codes for imputations for the Bayesian analysis will be used (see Section 6.2.2 and Section 6.2.4.1, respectively).

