6.3.4. Changes From Baseline in Percentage of Asthma Control Days (No Symptoms and No Rescue Medication Use) Over 12 Weeks From Week 1 Through 12 and Over 16 Weeks From Week 1 Through 16

An asthma control day is defined as a day on which the patient uses zero puffs of inhaled SABA, has no night-time awakenings, and experiences no asthma exacerbations.

The post-baseline analysis window for over 12 weeks will be from the first day of IMP up to the day 84. The post-baseline analysis window for over 16 weeks will be from the first day of IMP up to the day 112. Baseline window will include days up to the first dose of IMP.

Percentage of asthma control days in each analysis window will be calculated as

$$(\sum \text{asthma control days in an analysis window} / \text{number of non-missing e-diary days during the analysis window}) * 100$$

The changes from baseline in percentage of asthma control days over 12 weeks (up to day 84) and over 16 weeks (up to day 112) will be analyzed, respectively, using analysis of covariance (ANCOVA) including baseline percentage of asthma control days, randomization stratification factors, and treatment group in the model.

6.3.5. Change From Baseline in Clinic-Based Standardized Baseline-Adjusted Morning Trough FEV₁ at Week 16

The analysis will be based on data collected at site visits. FEV₁ measures at visit 1/screening, visit 3/DoR, visit 4/week 1, visit 5/week 2, visit 6/week 4, visit 7/week 8, visit 8/week12, and visit 9/week 16 or the early withdrawal visit. The analysis will include post-baseline data up to the visit 6/week 16. Baseline will be the last measure before the first dose of IMP.

The change from baseline in clinic-based morning trough FEV₁ at week 16 will be analyzed using MMRM method in a manner analogous to the analysis as described in Section 6.3.2. Baseline clinic-based morning trough FEV₁ will be used in model. WEEK will denote to the visit.

For model-based results, only week 16 results will be displayed. Summary statistics will be provided by visit/week.

6.3.6. Proportions of Patients Who Achieve Clinic-Based FEV₁ \geq 80% Predicted at Weeks 12, 16, and at Endpoint

The percent of predicted FEV₁ will be measured by handheld device. The analysis will be based on data collected at site visits and will be applied in patients with baseline FEV₁ $<$ 80% Predicted.

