6.3.8. Time to First Clinical Asthma Exacerbation (CAE) Throughout the Study

The time (days) to the first CAE is the interval from the randomization to the occurrence of the first CAE.

The observation for each patient is the interval from randomization to the occurrence of the first CAE, or censoring, whichever occurs earlier. It is derived as:

the date of censoring or the date CAE - the date of randomization + 1.

Patients who early terminated from the study without CAE due to lack of efficacy or an asthma-related AE will be also treated as experiencing CAE at the time of early withdraw visit.

Patients who complete the week 16 visit without CAE will be right-censored at the time of Week 16 visit. Patients without CAE and early withdrawn from the study before the week 16 with reasons other than lack of efficacy or asthma-related AEs will be right-censored at the time of early withdrawal visit.

The Kaplan-Meier (KM) method will be used to estimate and compare the distributions of time to the first CAE between treatment groups. Distribution difference will be compared by a log rank test adjusting for the randomization stratification factors.

[REDACTED]

6.3.9. Changes From Baseline in Asthma Control Questionnaire (ACQ-6) at Weeks 12 and 16

The ACQ-6 is a validated asthma assessment tool that has been widely used. The 6 questions are self-assessments (completed by the patient). Each item on the ACQ-6 has a possible score ranging from 0 to 6, and the total score is the mean of all responses. ACQ-6 will be administered at visit 2/run-in, visit 3/DoR, visit 5/week 2, visit 6/week 4, visit 7/week 8, visit 8/week 12, and visit 9/week 16 or early withdrawn visit.

The mean total score of the ACQ-6 is derived as the average of the individual item scores. For incomplete data, the following rules will apply:

1. Mean total score for a visit will not be calculated if Question 1 is left blank, irrespective of the completion of the remaining questions.
2. A missing score on post-baseline questionnaire for Questions 2-6 will be imputed based on the total scores from the previous visit, as long as at least 3 out of the 5 questions have responses for the current visit (ie, at least half of the remaining questions are answered).

The formula is: (total sum of non-missing scores for the current visit / total sum of scores for the previous visit for questions answered for the current visit) * (score for the missing question on the previous visit)

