16. APPENDIX

16.1.

[figure not shown]

16.2. Appendix B: Simulation Results to Assess the Bayesian Analysis using Multiple Imputations for Missing Data Handling

A random sample is taken from a previous study (CEP38072-AS-3082) comparing the safety and efficacy of another aIL5 product with placebo. The sample included 100 subjects in each treatment group for a total of 200 subjects with the following data: two stratification variables, baseline FEV₁ value, changes from baseline in morning trough FEV₁ at week 4, week 8, week 12 and week 16. The week 16 endpoint was used as the primary endpoint in this simulation.

The missing/observed data patterns from this sample are shown in [Table 7](#), which may be indicative of the missing data pattern in the current study. The patterns summarized include three categories: the complete cases, subjects with intermittent missing data, and subjects who had observations available prior to dropping out from study without further observations.

The results from the Bayesian analysis with multiple imputations for missing data handling, described in [Section 6.2.2](#), are compared with the analysis of covariance with multiple imputations. Two multiple imputation methods are used: 1) by treatment group (TRT-based); 2) using the control group data for both treatment groups (Control-based). [Table 8](#) below show the analysis results.

The results show that the Bayesian analysis and ANCOVA with multiple imputations produced similar results. This is expected because the Bayesian analysis uses non-informative priors for the mean and variance parameters. In addition, the treatment difference estimates using the control-based multiple imputations produced a smaller treatment effect, but it was similar to the result obtained with multiple imputations by treatment group. The control-based multiple imputation method is expected to be conservative for estimating the treatment effect. Since the overall percentage of missing data is small (<10% overall), the difference was small. As a result, the same conclusions can be made based on the posterior probability or the p-value.

In conclusion, the simulation study shows that the Bayesian analysis with multiple imputations method generates reliable estimates.

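### The visible MMRMs for clinic trough FEV₁ adjust for one pre-dose value only, although a closely comparable screening FEV₁ is already collected and could add precision

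*Protocol*

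**What the plan says.** The Protocol synopsis describes the supportive week 12 analysis in a sentence whose last terms run together: "The MMRM model will include baseline morning trough FEV₁, the randomization stratification factor (prior therapy use), baseline eosinophil count visit". For the same analysis, SAP 6.2.4.2 states: "The MMRM model will include baseline morning trough FEV₁, the randomization stratification factors (prior therapy use and absolute eosinophil count at screening". Protocol 9.5.4.2.1 has the same covariates. The week 16 analysis in SAP 6.3.5 follows the same pattern, with baseline clinic FEV₁ as the only FEV₁ term.

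SAP 4.2 fixes what baseline means: "baseline value is defined as the last observed value before the administration of IMP". For clinic spirometry that is normally the one session at V3. For handheld spirometry, by contrast, the same section uses a 7-day average.

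SAP 6.3.5 shows that two pre-dose clinic values exist: "FEV₁ measures at visit 1/screening, visit 3/DoR, visit 4/week 1, visit 5/week 2". It then takes the last one as baseline. The screening value is compulsory (Protocol 4.1, criteria e and f), and Protocol section 4 rules out eligibility waivers. Screening testing "will be conducted in the morning between 0530 and 1100 hours using the study-provided spirometry equipment", and Protocol 6.1.1 sets the same clock window at V3.

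The specification of the Bayesian primary analysis is redacted. The check of that method in SAP 16.2 lists "two stratification variables, baseline FEV₁ value, changes from baseline in morning trough FEV₁ at week 4" among its inputs, with one pre-dose FEV₁, but it uses data from a different study.

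**The concern.** One spirometry session mixes the patient's usual level with variation on the day. A second pre-randomisation session about two to four weeks earlier would normally help to separate the two, and so predict week 12 FEV₁ better than V3 alone. If so, the MMRM residual variance is larger than the collected data require, and the FEV₁ intervals are wider.

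Precision is not plentiful here. Planned power is about 80% at a one-sided 15% level, Amendment 01 loosened eligibility to help recruitment, and SAP 13.1.3 allows a reduction to 80 or 90 patients per arm.

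ACQ-6 offers a smaller parallel. SAP 6.3.9 says "ACQ-6 will be administered at visit 2/run-in, visit 3/DoR, visit 5/week 2", yet one baseline score enters the model. The V3 score is also the one on which patients are selected (≥1.5), so some regression to the mean is expected.

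**Working it through.** **1. Reproduce the plan's power.** SAP 2.4 gives an effect of 0.1 L, SD 0.35 L, a two-sample t-test at one-sided 15%, and "15% would provide a study power of 80.6"%. With 100 per arm and the dropout rates in Protocol 9.1 (15% placebo, 8% active), completers are 85 and 92.

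- SE = 0.35 × √(1/85 + 1/92) = 0.0527 L
- Power = Φ(0.1/0.0527 − 1.036) = Φ(0.863) = 80.6% (80.5% by noncentral t)

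The figure reproduces with no second covariate. The documents do not say whether 0.35 L is before or after adjustment for baseline.

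**2. Effect of the second covariate, equal correlations.** The documents give no correlations, so r is assumed. If screening, V3 and week 12 all correlate at r, residual variance with both values relative to V3 alone is (1 + 2r)/(1 + r)². Power below is by noncentral t at 85 vs 92, with 0.35 L read as the V3-adjusted SD (start 80.5%).

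| r | Variance ratio | SD (L) | Power |
|---|---|---|---|
| 0.5 | 0.889 | 0.330 | 83.5% |
| 0.7 | 0.830 | 0.319 | 85.2% |
| 0.8 | 0.802 | 0.314 | 86.0% |
| 0.9 | 0.776 | 0.308 | 86.8% |

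**3. Correlation that decays with time.** In general the ratio is 1 − (r_SW − r_VW·r_SV)² / [(1 − r_SV²)(1 − r_VW²)], with S screening, V V3 and W week 12. Take r_VW = 0.80 and r_SV = 0.85:

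| r_SW | Variance ratio | Power |
|---|---|---|
| 0.68 | 1.00 | 80.5% |
| 0.75 | 0.951 | 81.8% |
| 0.78 | 0.900 | 83.2% |

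The first row has no gain because 0.85 × 0.80 = 0.68: screening then says nothing about week 12 that V3 does not already say.

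**4. Stable patient level plus visit variation.** Assume between-patient SD 0.4 to 0.6 L, screening 3 weeks before V3, and SD of change 0.35 L. Let the within-patient variation be either independent between visits or 50% to 80% serially correlated (time scale 4 to 26 weeks). The variance cut is then about 5% to 21%.

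**5. Eligibility limits.** Simulations that restrict both pre-dose values to 40–85% predicted still show a gain. With independent visit variation (assumed mean 68%, between-patient SD 13 and within-patient SD 6 or 8 points) the ratios are 0.79 and 0.82. Under the structures in step 4 the cut is 7% to 18.5%.

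**6. If 0.35 L is the unadjusted SD of change.** Under step 4, V3 adjustment alone already brings the SD to, for example, 0.328 or 0.337 L. By the formula in step 1, power then goes from 83.9% to 85.4% (0.328 to 0.318 L) or from 82.5% to 88.2% (0.337 to 0.299 L). The starting point is higher than 80.6%, and the gain in these two examples is about 1.5 to 6 points.

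**7. ACQ-6.** With equal correlations of 0.5 to 0.8, the ratio in step 2 gives a cut of 11% to 20%.

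**The case against.** **The primary analysis.** A reader might infer that the Bayesian primary analysis itself discards precision, and so lowers the chance that 1200 mg reaches the 0.85 posterior threshold. The documents do not support this. The model specification is redacted, the amendment log holds only a fragment of superseded and revised wording, and SAP 16.2 describes a method check on another study. What can be shown concerns the MMRMs in SAP 6.2.4.2 and 6.3.5.

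**Comparability.** A reader might also infer that screening and V3 were measured under the same rules. That is only nearly true:

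- The patient's own rescue medication stops at V2, so screening and V3 fall under different rescue regimens.
- Several Appendix G washouts are timed to V2, so the text does not guarantee them at the screening test.
- Later tests are matched to within about 1 hour of the V3 clock time; screening is not.
- Screening spirometry may be repeated once in order to qualify.

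Each of these could make screening a weaker predictor than V3. They reduce the possible gain but do not make the covariate invalid.

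**Size.** The gain can be zero, and nothing in the documents excludes that. Zero does require that screening carry no information beyond V3. This is hard to reconcile with FEV₁ in litres, whose predicted value depends on age, height, sex and race, none of which is in the visible MMRM.

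**Status.** Adjusting for one baseline value and the stratification factors is valid, and the planned power holds without more. That stands.

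**Conclusion.** The point holds as a missed, low-cost gain in precision in the visible clinic FEV₁ MMRMs at weeks 12 and 16. It is not a bias, a contradiction or an error-rate problem.

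The defensible range for the reduction in residual variance is about 0% to 22%, with about 5% to 20% under structures that combine a stable patient level with visit-to-visit variation. Reading 0.35 L as the V3-adjusted SD, that is about 0 to 6 power points above 80.6%. If 0.35 L is the unadjusted SD of change, the V3-only start is already higher (82.5% and 83.9% in the examples of step 6).

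All gains rest on assumed correlations, and the power figures use the plan's two-sample calculation as a guide to the MMRM. Whether the primary analysis is affected cannot be determined from the public text.

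**What to change.** Before unblinding:

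- In SAP 6.2.4.2 and 6.3.5, add the qualifying screening pre-bronchodilator clinic FEV₁ as a second baseline covariate beside V3 FEV₁. Keep change from V3 as the endpoint. State which screening value is used when spirometry was repeated.
- For the imputation models and the Bayesian primary analysis (SAP 6.2.2), confirm whether the screening value is already included and add it if not.
- Optionally, add the V2 ACQ-6 score beside the V3 score in the ACQ-6 MMRM. V2 ACQ-6 is not an eligibility value and may be missing, so give a rule for that case.

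The cost is SAP wording and one extra parameter per model. No new data, visits or patients are needed. Missing FEV₁ covariates should not arise among eligible patients, because entry requires the screening value. As a pre-randomisation measurement, it does not bias the randomised comparison. The downside is that there may be no gain if screening adds nothing beyond V3.
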